## NON-INTERVENTIONAL (NI) STUDY PROTOCOL

### Study Information

Title	A Retrospective Observational Non-Interventional Study (NIS) to assess Patient Characteristics and Healthcare Resource Use (HRU) among COVID-19 Patients with or without Nirmatrelvir/Ritonavir (PAXLOVID™) treatment in the Kingdom of Bahrain.
Protocol number	C4671050
Protocol version identifier	1.0
Date	16 November 2023
Active substance	PF-07321332; ATC code J05AE30
Medicinal product	nirmatrelvir; ritonavir (PAXLOVID™)
Research objectives	
Primary objective:
 

1. To describe the baseline demographic and clinical characteristics, including pre-existing comorbidities, of adult COVID-19 patients treated with and those not treated with nirmatrelvir, ritonavir.

 
Secondary objectives:
 

1. To evaluate the number and proportion of COVID-19 patients who meet the most up-to-date WHO recommendations for the use of therapeutics in the treatment of COVID-19 (ie, version 14, published 10Nov2023) in comparison to Kingdom of Bahrain national recommendations.

2. To assess adult COVID-19 patients' HRU and outcomes within the 28-day period

PFIZER CONFIDENTIAL

CT24-WI-GL02-RF02 4.0 Non-Interventional Study Protocol Template For Secondary Data Collection Study

15-Jun-2022

Page 1 of 41

	
Exploratory objective:
 

1. Assess HRU and outcomes at day 5, 7 and 21 as exploratory analyses

Author	
[name] [REDACTED], MB Bch BAO(Ireland), MMM(USA), FACP(USA), FRCPC(Canada), PPD [REDACTED], Royal College of Surgeons in Ireland – Bahrain PPD [REDACTED] PPD [REDACTED], Bahrain Defence Force Hospital, Member of the National Taskforce for Combating the Coronavirus (COVID-19), Chairperson of the COVID-19 Control Room, Email: PPD [REDACTED]

This document contains confidential information belonging to Pfizer. Except as otherwise agreed to in writing, by accepting or reviewing this document, you agree to hold this information in confidence and not copy or disclose it to others (except where required by applicable law) or use it for unauthorized purposes. In the event of any actual or suspected breach of this obligation, Pfizer must be promptly notified.

## 2. LIST OF ABBREVIATIONS

Abbreviation	Definition
AE	Adverse Event
AEM	Adverse Event Monitoring
ATC	Anatomical Therapeutic Classification
BMI	Body Mass Index
CDC	Centers for Disease Control
COPD	Chronic Obstructive Pulmonary Disease
CRA	Clinical Research Associate
CT	Computed Tomography
DDI	Drug-drug interaction
DPIA	Data Protection Impact Assessment
eGFR	Estimated Glomerular Filtration Rate
EC	Ethics Committee
EHR	Electronic Health Record
ER	Emergency Room
EUA	Emergency Use Authorization
FDA	Food and Drug Administration

PFIZER CONFIDENTIAL

CT24-WI-GL02-RF02 4.0 Non-Interventional Study Protocol Template For Secondary Data Collection Study

15-Jun-2022

Page 5 of 41

Abbreviation	Definition
GDPR	Global Data Privacy Rule
GPP	Good Pharmacoepidemiology Practices
HRU	Healthcare Resource Utilization
ICD-10	International Classification of Diseases-10 th Edition
ICU	Intensive Care Unit
IPTW	Inverse Probability of Treatment Weighting
IMV	Invasive Mechanical Ventilation
IQR	Interquartile Range
I-SEHA	Kingdom of Bahrain National Health Information System
ISPE	International Society of Pharmacoepidemiology
LOA	List of Abbreviations
LOS	Length of Stay
NIH	National Institutes of Health
NIS	Non-Interventional Study
PCR	Polymerase Chain Reaction (COVID-19 test)
POS	Place of Service

Abbreviation	Definition
PSM	Propensity Score Matching
RCSI	Royal College of Surgeons in Ireland
RQ	Research Question
SD	Standard Deviation
STROBE	Strengthening the Reporting of Observational Studies in Epidemiology
US	United States
VOC	Variant of Concern
WHO	World Health Organization
YRR	Your Reporting Responsibilities

#### 4. ABSTRACT

Not applicable.

#### 5. AMENDMENTS AND UPDATES

None.

## 6. MILESTONES

Milestone and/or Deliverable Description (Provider must use Pfizer CT24 designated templates for Study Deliverables)	Planned Timeline/Dates
Draft study protocol	19 February 2023
Final study protocol	30 November 2023
Start of data collection	15 January 2024
End of data collection	15 February 2024
Start of data analysis	15 March 2024
End of data analysis	31 April 2024
Final Study Report	15 June 2024

## 7. RATIONALE AND BACKGROUND

In December 2019, COVID-19 was identified as a new, potentially fatal, respiratory infection caused by the novel coronavirus, SARS-CoV-2. The WHO declared COVID-19 a Public Health Emergency of International Concern on 30 January 2020 and further characterized the disease outbreak as a pandemic on 11 March 2020. As of 01 January 2022, more than 289,000,000 cases have been confirmed worldwide, and at least 5,440,154 deaths have occurred. Despite widespread use of COVID-19 vaccine since 2020 in Bahrain, COVID-19 caused 702830 cases, 26194 hospitalizations and 1546 deaths during the period 2020-2023 in Kingdom of Bahrain.

The clinical presentation of COVID-19 varies widely, ranging from an asymptomatic infection to critical illness characterized by respiratory failure, septic shock and other multiple organ dysfunction or failure. Although the majority of cases are asymptomatic or mild, patients who are hospitalized with COVID-19 may have significant morbidity and mortality. Between February 2020 and September 2021, the United States CDC estimated that of a total of 146.6 million infections, 85% of patients were symptomatic and only 5% required hospitalization for treatment.

According to the NIH guidelines, management of non-hospitalized patients with acute COVID-19 should include supportive care, advise on when to contact a health care provider and seek an in-person evaluation, and COVID-19 specific therapy for patients who have a high risk of disease progression. More specifically, non-hospitalized patients with mild-to-moderate COVID-19 who are at high risk of clinical progression may receive (listed in order of preference) nirmatrelvir (PF-07321332)/ritonavir (Paxlovid™), sotrovimab, remdesivir, or molnupiravir.

## Kingdom of Bahrain:

Kingdom of Bahrain is one of the leading countries in COVID-19 outpatient treatment care. A unique outpatient clinic has been established in May 2021 to provide outpatient care for patients with positive Coronavirus. Treatment including monoclonal antibodies such as Bamlamivimab, Regen-Cov, Sotorovimab and Paxlovid™ are offered for all high-risk and close contact patients, such treatments are in line with the guidelines of the FDA.

The clinic has a dedicated call center providing different services to ease the patient treatment process and provides follow-up care. The overall aim of the clinic is to target mild to moderate high risk COVID-19 patients and provide outpatient treatment as early as possible to reduce disease progression, including hospitalization and death.

On 01 January 2022, the National Health Regulatory Authority (NHRA) approved the emergency use of Paxlovid™ for mild-moderate cases who are at high risk – identified as per WHO definition of high-risk group – of developing severe COVID-19. Since approval, Paxlovid™ has been established as the first line therapy along with Sotrovimab in the Kingdom of Bahrain.

In the EPIC-HR trial, Paxlovid™ reduced the risk of hospitalization or death by 88% compared to placebo in non-hospitalized adults with laboratory-confirmed SARS-CoV-2 infection and a risk factor for progression to severe disease, when treatment was initiated within 5 days of symptom onset. Other efficacies reported for COVID-19 therapies, include sotrovimab (ie, 85% relative reduction reported), and remdesivir (ie, 87% relative reduction reported) and molnupiravir (ie, 30% relative reduction reported). Furthermore, *in vitro* analyses, suggested that Paxlovid™ is active against the B.1.1.529 (Omicron) variant of concern (VOC).

COVID-19 has put significant pressure on the healthcare system worldwide and caused an enormous economic burden to society. While patient characteristics, healthcare resource utilization (HRU) and healthcare costs of patients hospitalized with COVID-19 have previously been described in US studies, such data are limited among non-US countries. Furthermore, while the majority of current research focuses on hospitalized COVID-19 patients, little is known about COVID-19 patients identified in an outpatient setting.

The availability of antiviral treatments in the outpatient setting, such as Paxlovid™, have potential to complement vaccination strategies during the COVID-19 pandemic and further reduce the burden on healthcare system capacity in the short- and long-term. There is a need to identify patients in the real-world setting globally, who are diagnosed with COVID-19 and may be at an increased risk of healthcare resource utilization, as prior literature suggests these patients are most likely to benefit from outpatient therapies. With the authorization (ie, EUA) of Paxlovid™, there is also a growing need to complement clinical trial findings and address data gaps by generating real-world evidence that may help inform healthcare decision-making globally during this early EUA utilization phase.

This study aims to describe the characteristics, outcomes and treatment patterns of COVID-19 patients, who are receiving Paxlovid™ in Bahrain according to the local drug label.

## **8. RESEARCH QUESTION AND OBJECTIVES**

The aim of this study is to describe the baseline demographic and clinical characteristics, and HRU of adult ( $\geq 18$  years) COVID-19 patients who have been prescribed nirmatrelvir, ritonavir treatment in the outpatient setting.

Primary objective:

1. To describe the baseline demographic and clinical characteristics, including pre-existing comorbidities, of adult COVID-19 patients treated with and those not treated with nirmatrelvir, ritonavir.

Secondary objectives:

1. To evaluate the number and proportion of COVID-19 patients who meet the most up-to-date WHO recommendations for the use of therapeutics in the treatment of COVID-19 (ie, version 14, published 10Nov2023) in comparison to Kingdom of Bahrain national recommendations.
2. To assess adult COVID-19 patients' HRU and outcomes within the 28-day period

Exploratory objective:

1. To assess HRU and outcomes at day 5, 7 and 21 as exploratory analyses

## **9. RESEARCH METHODS**

### **9.1. Study Design**

This will be a retrospective observational cohort study of patients diagnosed with COVID-19 in the Kingdom of Bahrain. Treated patients are defined as those have been prescribed nirmatrelvir, ritonavir and managed in the outpatient setting (eg, receiving medical treatment without being admitted to a hospital for COVID-19) while control group is those not treated with nirmatrelvir, ritonavir. Data will be from the *I-Seha electronic medical records* and descriptive analyses will be conducted for these two cohorts and will compare healthcare resource use in patients treated with nirmatrelvir, ritonavir and those not treated with nirmatrelvir, ritonavir.

**Table 1. Cohort Definitions**

Name	Criteria	Identification Period	Index Date	Follow Up Period
Treated patients	Patients diagnosed with COVID-19 and treated with Paxlovid™	After Paxlovid™ availability during the same dominant variant (ie, Omicron or Delta etc.) era timeframe as Cohort	Paxlovid™ prescription written date or dispense date*  If neither of the above are available, the COVID-19 diagnosis date may be used as the index date	28 -days follow up
Control group	Patients diagnosed with COVID-19 and not treated with Paxlovid™	After Paxlovid™ availability during the same dominant variant (ie, Omicron or Delta etc.) era timeframe as Cohort	Date of COVID-19 diagnosis	28 -days follow up

\*If both dates are available in the data source, the most recent date should be used as the index date for Cohort.

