### 9.2.2. Exclusion Criteria

**There are no exclusion criteria for this study.**

## 9.3 Variables

The following variables are used to obtain comprehensive descriptive results.

1. Demographics
2. Date of symptoms
3. Viral variant analysis where available (type of viral variant ie, omicron, delta etc.)
4. PCR date along with CT Value

5. Co-morbidities and
6. BMI if  $\geq 30$
7. Symptoms at presentation
8. COVID 19 vaccine status (NB 92% of population has been vaccinated -with at least one dose of COVID 19 vaccine- in Bahrain)
9. Hospital admission
10. Follow up looking at compliance and reason of non-compliance
11. Day 5,7, 21 and 28 symptoms for COVID-19 patients who receive and HRU limited to admission (ICU, ward, need for oxygen therapy) or death
12. Date of symptoms resolution if applicable

**Table 2** Table 2 below depicts the patient demographics that will be accessed during the baseline and follow-up periods. The baseline period is defined as one year before the index date. Comorbidities (full list in [Table 6](#)) and maintenance medication usage for chronic conditions (eg, statins, antihypertensives, etc.) will be described during the baseline period and follow-up periods and are listed in [Table 3](#).

Risk factors for severe COVID-19, intensive care unit (ICU) usage, invasive mechanical ventilation (IMV) usage, supplemental oxygen use, non-invasive ventilation, and high-flow nasal cannula usage are depicted in [Table 5](#) and will be extracted from the *I-Seha* national electronic health record database.

Where applicable, emerging treatment patterns may be assessed as the time from symptom onset to COVID-19 diagnosis, time from symptom onset to treatment initiation, and the time from COVID-19 diagnosis to treatment initiation as illustrated in [Table 5](#).

10Nov23 WHO recommendations for Paxlovid treatments to define: 1. COVID-19 patients who meet the WHO criteria for “strongly recommended” 2. COVID-19 patients who meet the WHO criteria for “conditionally recommended”, and 3. COVID patients who are not falling into categories 1 or 2 will be used.

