**Table 8. [SAMPLE] Results Table**

	Treated COVID-19 patients (N = n)	Control Group	Untreated COVID-19 patients (N = n)
Baseline Variables			

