## 1.1 STUDY DESIGN

This study is a retrospective cohort study examining COVID-19 patients who were treated with Paxlovid. It will also include a control group of COVID-19 patients who were offered, but refused, Paxlovid. It will involve a secondary data analysis of patient data from the ISeha electronic medical records.

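### Outcomes are compared with one pooled control group defined by not taking Paxlovid, with no split by other active COVID-19 therapy such as sotrovimab

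*Protocol*

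**What the plan says.** **Control definition.** Protocol 9.1 sets the treated group against the rest: "while control group is those not treated with nirmatrelvir, ritonavir". Protocol Table 1 words it as "Patients diagnosed with COVID-19 and not treated with Paxlovid™". SAP 1.1 is narrower: "It will also include a control group of COVID-19 patients who were offered, but refused, Paxlovid". Protocol 9.2.2 adds "There are no exclusion criteria for this study". None of these passages mentions other COVID-19 therapy.

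**Setting.** Protocol section 7 (repeated in the SAP introduction) states: "Since approval, Paxlovid™ has been established as the first line therapy along with Sotrovimab in the Kingdom of Bahrain". The same section describes an outpatient clinic that offers bamlanivimab, Regen-Cov, sotrovimab and Paxlovid.

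**Comparison.** Protocol 9.1 plans to compare healthcare resource use (HRU) between the two groups. SAP objective (iv) examines outcome differences. SAP 1.12 and 1.13 apply significance tests, 95% confidence intervals and effect sizes. SAP Table 7 has two data columns, Paxlovid and Control.

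**Other therapy.** Protocol Table 5 and SAP Table 4 record antibody use (tocilizumab and bamlanivimab/etesevimab are named) and antiviral use (remdesivir, Paxlovid, molnupiravir) over baseline and follow-up. Protocol 9.3 sets baseline at one year before the index date. SAP Table 7 reports these in one row covering antivirals, Paxlovid and COVID-19 antibodies together. The sample results table, Protocol Table 8, carries the heading "Untreated COVID-19 patients".

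**The concern.** Refusing Paxlovid is not the same as going untreated. Where a second first-line drug and other antibodies are on offer to the same high-risk patients, some refusers could have taken one of them. If so, the control column averages outcomes over patients with no therapy and patients on another active therapy.

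The resulting difference would describe neither Paxlovid against nothing nor Paxlovid against an alternative. Its size would depend on the local mix, and a reader of the results could mistake it for an effect relative to no treatment. This matters more because the SAP attaches p-values and confidence intervals to these contrasts.

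**Working it through.** **1. Does any analysis step separate controls by other therapy?**
- Exclusions: none (Protocol 9.2.2).
- Subgroups and covariates: both not applicable (SAP 1.8 and 1.11).
- Propensity-score characteristics (SAP 1.13): age, sex, vaccination, high-risk status, care-seeking, socioeconomic factors, residence and comorbidities. Other COVID-19 therapy is not listed.
- SAP Table 7: a single control column.

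So nothing restricts, matches on or splits by it.

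**2. Can the mix be recovered from the medication row in SAP Table 7?** Only in part. No control has Paxlovid, so the row in the control column would show the share with some other antiviral or antibody. Four things limit it:
- It pools all agents, and the Paxlovid column will sit near 100% by construction, which hides additional agents there.
- The antibody definition does not name sotrovimab or Regen-Cov. The list may not be meant as exhaustive, but extraction cannot rely on that.
- Use is counted over a one-year baseline plus follow-up. An antibody from an earlier episode, one given at the refusal visit and remdesivir given after admission all count alike.
- A percentage, however accurate, does not separate the outcomes of the two kinds of control.

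**3. How much could the mix matter?** The plan has no effect or power figure to reproduce; the study size is a feasibility count (8263 eligible, at least 3000 treated, 1000 not).

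Inputs from Protocol section 7: relative reductions of 88% for Paxlovid and 85% for sotrovimab. Let *s* be the share of controls given sotrovimab (not in the documents, so shown from 0 to 1) and *p0* the risk without therapy.

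- Treated risk = p0 × (1 − 0.88) = 0.12 p0
- Control risk = p0 × (1 − 0.85 s)
- Risk ratio = 0.12 / (1 − 0.85 s), which does not depend on p0

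| s | 1 − 0.85 s | Risk ratio | Risk difference, p0 = 3% (points) | Risk difference, p0 = 6% (points) |
|---|---|---|---|---|
| 0 | 1.0000 | 0.12 | 2.64 | 5.28 |
| 0.25 | 0.7875 | 0.15 | 2.00 | 4.00 |
| 0.50 | 0.5750 | 0.21 | 1.37 | 2.73 |
| 0.75 | 0.3625 | 0.33 | 0.73 | 1.46 |
| 1 | 0.1500 | 0.80 | 0.09 | 0.18 |

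For example, at s = 0.5 and p0 = 3%: 0.03 × 0.575 − 0.03 × 0.12 = 0.01725 − 0.0036 = 0.01365.

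The 3% and 6% are the WHO moderate-risk and high-risk hospitalization rates in Protocol 9.7. Using them as untreated risks is an assumption.

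**4. Sensitivity.**
- If the other agent were molnupiravir (quoted reduction 30%), the risk ratio at s = 1 is 0.12 / 0.70 = 0.17, so the mix hardly matters.
- If both drugs had an assumed 50% reduction, the risk ratio is 0.50 / (1 − 0.50 s): 0.50 at s = 0, 0.67 at s = 0.5 and 1.00 at s = 1.
- In every case the shift is toward no difference and the direction does not reverse.

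**The case against.** The best defence is that the study is descriptive. The protocol limits itself to association, the SAP states no hypotheses and calls the work exploratory, and Paxlovid versus no Paxlovid among patients who were offered it is a coherent contrast. That stands: the comparison can be interpreted as long as it is labelled for what it is. It does not remove the need for the label or the split, because the SAP still tests outcome differences.

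Several stronger readings are tempting, and the documents do not support them:
- *The mix is unreported.* SAP Table 7 does have a medication row by group. It is too coarse, but it exists.
- *Controls did receive sotrovimab.* Nothing shows that any did; only availability is documented.
- *The protocol claims that controls are untreated.* The heading appears in a table marked as a sample, whose column layout cannot be read reliably from the extracted text. The SAP shells simply say Control.
- *Secondary objective 2 is a comparison.* It only assesses HRU and outcomes over 28 days. The contrast comes from Protocol 9.1 and SAP objective (iv).
- *The comparator must be patients with no therapy.* That is a different question, and the sponsor may reasonably keep all refusers as the main comparator.

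**Conclusion.** The concern holds as a gap in comparator definition and reporting. As planned, HRU and outcomes are averaged over controls whatever other COVID-19 therapy they had, and the tables would not let a reader undo that.

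On the quoted efficacies the expected risk ratio runs from 0.12 to 0.80 as the sotrovimab share goes from 0 to 100%. The change is modest up to a 50% share (0.21) and large only when most controls had the drug. The 0.80 needs every refuser to have taken sotrovimab and should not be read as an expected value.

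The calculation assumes that the quoted reductions carry over to this population and to the same outcome (the endpoint of the 85% is not stated), that the groups are otherwise comparable, and that Paxlovid patients had no second agent. The actual size is unknown because the share is unknown. The plan should be changed, but the gap does not invalidate the study.

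**What to change.** 1. Add sotrovimab and Regen-Cov to the antibody variable (Protocol Table 5, SAP Table 4). For each agent record the start date and whether it was given as an outpatient or inpatient.
2. In SAP Table 7, replace the pooled antiviral and antibody row with one row per agent, by group.
3. Keep the all-controls comparison and label it 'no Paxlovid', not 'untreated', including in Protocol Table 8. Beside it, give the objective (iv) outcomes split by outpatient COVID-19 therapy started at the offer or refusal visit: none versus other. Apply the same restriction to Paxlovid patients who also had another agent. Restricting only the controls would be asymmetric and could favour Paxlovid.
4. Do not classify patients on inpatient remdesivir or tocilizumab, because those follow the outcome.

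**Cost.** One or two extra extraction fields in a chart review that already covers all 8263 records, some additional table rows and columns, and smaller control subgroups with wider intervals. Wording changes alone would not be enough, because the present variables do not place therapy at the offer visit.
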